## 11.0 Number of Participants

### 11.1 *Number of Participants to be Consented:*

To demonstrate the preliminary effectiveness of the intervention we recruited approximately 20 facilities within which an estimated 8 eligible providers work. For the baseline visits a total of 160 unannounced SP visits were made, or about 8 visits per clinic. Given the nature of patient intake procedures at outpatients facilities of the type that our SPs will visit, we were unable to control which of the consented providers in a given facility consented to SP visits. It is therefore possible that some consented providers in these clinics will never receive an unannounced SP visit, while others may receive multiple visits.

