#### 17.2 Power Analysis:

**Stigma Quantification:** The primary objective of this pilot study is to estimate the extent to which stigma towards PLWH (HIV stigma) and towards MSM (homophobia) contribute to the deterioration of healthcare quality relative to straight people without HIV. A total sample size of 160 standardized patient (SP) interactions would provide 80% power (alpha=0.05) to detect a minimum effect size of 0.18 standard deviation. This calculation is conservative in that it does not account for blocked randomization of the SP cases within practices, which will lend additional power to each comparison. Two-sided tests will be needed to detect differences across the four case scenarios in order to separately quantify HIV, sexual, and intersectional stigma, for which the same assumptions will provide the same amount of power to identify a minimum effect size of 0.17 standard deviation between any 2 pairwise comparisons of scenarios. As recruitment will take place at the clinic level, the number of participants that will be needed to be recruited to the study will depend on estimates of the average numbers of eligible providers that our team can reasonably expect to recruit at each clinic. Preliminary data suggest that clinics in our study region employ an average of 5 eligible providers, of whom we conservatively expect to recruit 70% or 3.5 per clinic. Each provider will receive 3 unannounced visits from a standardized patient, yielding a final estimated pool of 56 providers for this study.

**Preliminary intervention effects:** A secondary goal of the RCT is to estimate the preliminary effect of the intervention on quality of care index observed by SPs. Though this is only a secondary goal, we determine that it is plausible that the target enrollment of 20 clinics randomly allocated to treatment and control in a 1:1 manner could yield sufficient power to detect reasonably small effects on the primary outcome measure. That is, with an alpha level of 0.05 for a one-sided test, an intra-cluster coefficient of 0.07, and a baseline prevalence of standardized quality of care index (with mean of 0 and standard deviation of 1), a sample size of 160 SP clinic visits (8 visits per clinic on average) would provide 80% power to detect a reduction in EOC scores due to the intervention as small as 0.17 standard deviations.

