#### 17.3 Statistical Analysis:

**Stigma Quantification:** Each of the four SP scenarios will be coded across two binary variables ("MSM" and "HIV") that will separately account for whether same-sex behaviors, HIV+ status, or both were announced by the SP during the provider visit. The scenarios will then be regressed on the quality of care index to assess the excess erosion of care observed in visits where SPs present as both HIV infected and as MSM, beyond the simple sum or product of the erosion experienced with only one of the attributes. Specifically, we will estimate:

$$\theta_{ijs} = \alpha + \beta_1 HIV_{ij} + \beta_2 MSM_{ij} + \beta_3 (HIV_{ij} * MSM_{ij}) + \gamma_j + \eta_s + \varepsilon_{ijs}$$

where  $\theta_{ijs}$  is the quality of care index as measured in SP interaction  $i$  in facility  $j$  conducted by SPs;  $HIV_{ij}$  is an indicator for the HIV status of the SP scenario in that given provider encounter;  $MSM_{ij}$  an indicator for the MSM status of the SP scenario in that given provider encounter;  $\gamma_j$  is a vector of facility fixed effects; and  $\eta_s$  is a vector of fixed effects for SPs. Here,  $\beta_1$  and  $\beta_2$  provides an estimate of HIV and

PROTOCOL TITLE: Standardized Patients to Address Intersectional Stigma  
 VERSION DATE: 07/23/2019

MSM stigma respectively, and  $\beta_3$  the estimate of stigma due to the presence of both HIV and MSM status.

Preliminary intervention effects: We will estimate the main intention-to-treat (ITT) impact of the training intervention using the Ordinary Least Squares (OLS) regression:

$$\theta_{idc} = \beta_0 + \beta_1 T_c + \beta_2 \bar{\theta}_{dc(t-1)} + \gamma X_{ic} + \varepsilon_{idc}$$

where  $\theta_{ict}$  is the healthcare quality index from SP interaction  $i$  with doctor  $d$  in clinic  $c$  measured at follow-up,  $T_c$  is a dummy variable that takes the value of 1 if the clinic was randomized to be offered training and 0 if in the control group. The coefficient of interest is  $\beta_1$ , which captures the ITT effect of training on the quality of care. We control for the average quality index from all SP interaction with doctor  $d$  at baseline,  $\bar{\theta}_{dc(t-1)}$ , as well as a vector of SP and disease script type (varying HIV and MSM status) fixed effects.  $\varepsilon_{idc}$  represents the idiosyncratic error, which we cluster at the clinic, the level of randomization.

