The ITT impacts reflect the effect of physicians being *offered* an opportunity to participate in training, not the causal effect of training itself. We therefore also estimate the effect of participating in training using the model

$$\theta_{idc} = \pi_0 + \pi_1 A_{dc} + \pi_2 \bar{\theta}_{dc(t-1)} + \varphi X_{ic} + \nu_{idc}$$

where  $A_{dc}$  is a measure of whether or not doctor  $d$  in clinic  $c$  attends the training and other variables are defined as above. We fit this equation by two-stage least squares (2sls) using the following first-stage equation:

$$A_{dc} = \delta_0 + \delta_1 T_c + \delta_2 \bar{\theta}_{dc(t-1)} + \zeta X_{ic} + \mu_{idc}$$

where the excluded instrument is the treatment assignment of doctor  $d$ 's clinic,  $T_c$ . We interpret the coefficient  $\pi_1$  as the local average treatment effect, or LATE, of participating in training on the quality of care provided.

While the analysis outlined above provides estimates of the effect of the training (or offer of training) on the quality of care provided to SPs presenting with cases of presumptive syphilis, the goal is to estimate the effect of the training on *enacted stigma*. That is, rather than the overall effect on the level of healthcare quality, we are primarily concerned with observing how the training affects the difference in the quality of care received by patients presenting as MSM or HIV-positive vs. those not, all else equal. Our two levels of randomization (SP-doctor interactions disease script types and clinics to treatment or control) allow us to estimate the causal effect of training offer (or participation) by estimating regressions analogous to the above, but interacting the dummy clinic treatment allocation with dummy variables for each SP script type. For ITT effects, we estimate

$$\theta_{idc} = \alpha_0 + \alpha_1 T_c + \alpha_{11} T_c \times V^{HIV+,MSM-} + \alpha_{12} T_c \times V^{HIV-,MSM+} + \alpha_{13} T_c \times V^{HIV+,MSM+} + \alpha_2 \bar{\theta}_{dc(t-1)} + \gamma \Gamma_{ic} + \varepsilon_{idc}$$

Where  $V$  are dummy variables for three of the four script variations (leaving out the HIV-, MSM- variation).  $\Gamma_{ic}$  is a vector of SP fixed effects. The coefficients  $\alpha_{11}$ – $\alpha_{13}$  represent the effect of training offer on the *difference* in healthcare quality provided

PROTOCOL TITLE: Standardized Patients to Address Intersectional Stigma  
VERSION DATE: 07/23/2019

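### Section 17.3 clusters on about 20 clinics without naming a small-sample method (a cheap improvement); separately, its interaction equation as printed omits the case-script main effects (wrong as written)

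*Combined protocol and SAP*

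**What the plan says.** Section 17.2 sets the design for the training effect as a "target enrollment of 20 clinics randomly allocated to treatment and control in a 1:1 manner", "with an alpha level of 0.05 for a one-sided test", with an intra-cluster coefficient of 0.07 and 160 visits ("8 visits per clinic on average"). It ranks the aim: "A secondary goal of the RCT is to estimate the preliminary effect of the intervention".

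Section 17.3 fits OLS with a treatment indicator and a doctor-level baseline ("We control for the average quality index from all SP interaction with doctor"). It adds fixed effects for SP and for case script, and its error "represents the idiosyncratic error, which we cluster at the clinic, the level of randomization". It gives no finite-sample factor, critical values, degrees of freedom or sidedness for beta_1. Section 2.4 promises a fuller analysis plan before analysis starts but gives none of its content.

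Later in 17.3, an interaction equation multiplies treatment by dummies for three of the four case scripts. Its only other terms are the intercept, treatment, the doctor baseline and a vector Gamma, which "is a vector of SP fixed effects". Script dummies do not appear on their own.

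**The concern.** Cluster-robust standard errors tend to be too small when there are few clusters. The finite-sample factor and the reference distribution are two separate choices, and 17.3 leaves both open. Two analysts could follow the text, obtain the same beta_1 and report different p-values and intervals. The choice could also be made after seeing the data.

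The interaction equation is a different kind of problem. Section 17.3 says that its main interest is how training changes the gap in care between scripts. An equation without script main effects does not estimate that change. It can report that training altered stigma when training did nothing.

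**Working it through.** **Plan's own figure.** The plan states no error rate to reproduce. Its one figure for this comparison, 0.17 SD detectable at 80% power, does not follow from the inputs in 17.2. The design effect is 1 + 7 × 0.07 = 1.49, the standard error is √(4 × 1.49/160) = 0.193, and (1.645 + 0.842) × 0.193 = 0.48 SD. That is a separate matter. Here 0.17 serves only as an assumed size for a script deficit.

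**Part 1: beta_1, by hand.**
- G = 20 clinics and N = 160 visits (17.2); 8 SPs and 4 scripts (12.1).
- K = 13 coefficients: intercept, treatment, baseline, 7 SP dummies, 3 script dummies.
- Usual factor: G/(G−1) × (N−1)/(N−K) = 20/19 × 159/147 = 1.139. Its square root is 1.067, so it lengthens the standard error by 6.7%.
- Two-sided critical values are 2.093 for t(19) and 1.960 for the normal, a ratio of 1.068.
- Between the two extreme readings, interval width differs by 1.067 × 1.068 = 1.14.

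**Part 1: beta_1, by simulation.** There is no training effect; total variance is 1, ICC 0.07, and every clinic has 8 visits. The fitted model is the ITT model of 17.3. Assumptions not in the documents are normal errors, the number of doctors per clinic, the correlation between baseline and follow-up clinic effects, and filling a missing doctor baseline with the clinic mean. Ranges are over runs of 4,000 to 20,000 trials with differing assumptions; the Monte Carlo standard error near 5% is about 0.22 points at 10,000 trials.

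| Reading of 17.3 | One-sided 5% | Two-sided 5% |
|---|---|---|
| Usual factor, t(19) | 5.0–5.6% | 5.2–5.4% |
| Same factor, normal values | 5.7–6.7% | 6.6–6.9% |
| No factor, normal values | 7.0–7.9% | 8.0–8.8% |
| CR2, Satterthwaite df | 5.0–5.1% | 5.0–5.1% |

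Dropping visits to doctors with no baseline, with 8 still planned per clinic, changes little: 5.2–5.4%, 6.7% and 8.2–8.9% two-sided for the first three rows.

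For sensitivity only, suppose visits per clinic vary. Two-sided rates, in the table's order, are 5.8/7.2/8.9/5.4% with a coefficient of variation (CV) of 0.2, 6.2/7.9/9.6/5.5% with 0.4, and 6.8/8.5/10.4/5.4% with 0.65.

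**Part 2: the interaction equation, by hand.** Set the baseline and SP terms aside.
- Control arm: every script has fitted mean alpha_0.
- Treated arm: the reference script has mean alpha_0 + alpha_1, and script k has alpha_0 + alpha_1 + alpha_1k.
- So alpha_1k is the treated-arm mean for script k minus the treated-arm mean for the reference. The control arm's script gap is never subtracted.

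Now give each non-reference script a deficit of 0.17 SD in both arms, with no effect of training. The true change in the gap is 0, but alpha_1k centres on −0.17. There are 80/4 = 20 visits per script per arm, so its standard error is about √(2 × 0.93/20) = 0.305. The ratio is 0.17/0.305 = 0.56, and the two-sided rejection rate is about Φ(−1.40) + Φ(−2.52) = 8.0% + 0.6% = 8.6%, before any few-clusters inflation.

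**Part 2: by simulation**, with SP and baseline terms in the model and 8 visits per clinic:

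| Interaction model | Mean estimate (truth 0) | Factor, t(19) | CR2 |
|---|---|---|---|
| As printed | −0.17 | 9.7–10.5% | 7.3–7.9% |
| Script main effects added | 0.00 | 4.7–5.4% | 4.4–5.1% |

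CR2 corrects the standard error, not the quantity being estimated, so it cannot repair the printed equation.

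**The case against.** The best case against Part 1 is that there is hardly a problem. Under the usual convention and equal clinics, the rate is about 5.2% two-sided against about 5.1% with CR2, a gap within simulation error. The training effect is a secondary aim of a pilot, and the plan promised in Section 2.4 is a natural place for such detail. Stating the usual factor with t(G−1) would also end the ambiguity. All of this stands, and it is why Part 1 is a cheap improvement and not a flaw in the design.

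A reader might infer that the test will run at 7–9% one-sided, or above 10% two-sided. The documents do not support that. No section chooses an uncorrected standard error or normal values, and the highest figures also need uneven visits per clinic. Section 11.1 says that "a total of 160 unannounced SP visits were made, or about 8 visits per clinic", and 17.2 gives only an average. The lack of control described in 11.1 concerns which doctor is seen, not how many visits a clinic receives. Uneven clinics are therefore an assumption.

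Nor is CR2 exact. In one run with 4 to 12 visits per clinic its one-sided rate was 5.7%, against 6.4% with the usual factor and t(19).

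On Part 2, 17.3 presents the interaction regressions as analogous to the main model, which does contain script effects, so the authors may intend them. But Gamma is redefined as SP effects alone, and an analyst who follows the equation will leave them out. A reader might also infer that false findings are certain. They are not: the excess depends on script differences that this document does not report, and 0.17 SD is assumed.

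**Conclusion.** Two conclusions of different weight.

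1. Section 17.3 leaves the small-sample method and sidedness for beta_1 open. With about 8 visits per clinic, the error rate is about 5% one-sided and 5.2% two-sided under the usual factor with t(19), about 6% and 7% with normal values, and about 7% and 8% with no factor and normal values. This rests on 20 clinics, ICC 0.07 and the simulation assumptions above. It is worth fixing because it costs almost nothing.

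2. The interaction equation is wrong as written. Its terms absorb script differences common to both arms. With an assumed 0.17 SD deficit and no training effect, each term rejects about 10% two-sided (about 7% with CR2), against about 5% with main effects included. The excess grows with the true script gap and vanishes only if there is none.

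**What to change.** **Tests and intervals.** Keep the OLS model and the beta_1 estimate. State in 17.3, or in the analysis plan promised in Section 2.4, that p-values and confidence intervals for beta_1 and for the treatment-by-script terms use CR2 clinic-clustered standard errors with Satterthwaite degrees of freedom. At minimum, name the finite-sample factor with t(G−1), and never normal values. State whether each test is one- or two-sided. For the 2SLS analysis, which has a single instrument, take the test of no effect from the ITT reduced form by the same method.

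This needs a few sentences and no new data. Compared with the usual factor and t(G−1), beta_1 intervals are about 1% wider when every clinic has 8 visits, and up to about 8% wider if visits are very uneven (CV about 0.65).

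**Interaction equation.** Add the three script dummies V as main effects. No new data are needed, but the alpha_11 to alpha_13 estimates change and become less precise. By the same hand calculation, the standard error goes from √(2 × 0.93/20) = 0.305 to √(4 × 0.93/20) = 0.431, a factor of √2. The precision given up was obtained only by assuming that scripts do not differ in the control arm.

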By contrast our experimental SP audit method provides a window of insight into provider behaviors *as they unfold in real clinical settings*, providing an objective and standardized measure of stigma amenable to comparison across studies and settings. Our SPs will be recruited from among MSM living locally, whose group makeup will be managed to reflect the overall characteristics of the local MSM community in terms of age, ethnicity, and socioeconomic status. SPs will be trained to consistently present a standardized case to providers. Using an experimental audit design, we will randomly vary the HIV infection status and sexual orientation of all of our SPs. Stigma will be evaluated by comparing the quality of care that SPs experience during provider visits. Quality of care will be measured by administration of a standard of healthcare checklist to SPs following each visit, and which will include items related to provider behaviors including the types of questions asked, accuracy of the preliminary diagnosis, body language and bedside manner (checklist included in Appendix 1). Differences in tallied aggregate scores across SP visit scenarios (e.g. HIV positive versus HIV negative presentations) will be quantified as the enacted healthcare stigma attributable to the condition in question (i.e. HIV infection). In addition, SPs will participate in post-visit “debrief sessions” with another member of the study staff immediately following each visit to recount any other possible features of the visits—both positive and negative—not accounted for in the healthcare quality checklist. This method of quantifying stigma will not be used to identify individual providers or

PROTOCOL TITLE: Standardized Patients to Address Intersectional Stigma  
VERSION DATE: 07/23/2019

instances of poor treatment but rather to characterize population level incidence and patterns of stigma enacted by providers towards vulnerable patients. Lastly, the impact of the intervention on overall HIV testing volumes in study facilities will also be evaluated by examining aggregate counts of facility-level HIV tests conducted during the baseline and follow-up observation periods. This information will be provided by the laboratory departments of all participating facilities. This technique of data collection has been successfully piloted with a clinic-based intervention administered by the GDCDC.

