## 12.0 Recruitment Methods

### 12.1 *Recruitment Process:*

Sampling of study facilities will take place across the 46 candidate STD practices across the Guangzhou metro area (Fig 2) and which meet our eligibility criteria of 1) having formal government accreditation as a medical center (a basic tenet of all public hospitals in China); and 2) possession of an accredited on-site laboratory with capacity to provide enzyme-linked immunosorbent assay testing for HIV, treponemal (e.g. Treponema pallidum particle agglutination) and non-treponemal tests (e.g. rapid plasma regain) for syphilis. Sampling will be conducted using a stratified approach to sample evenly across the 11 districts of Guangzhou city which includes urban and rural areas in order to maximize comparability between arms. Sampling will also consider travel distance between study facilities in order to minimize risk of contamination across arms following the intervention. Lastly, twice the number of facilities as needed for the final sample size will be screened and randomized in anticipation of the fact that a subset of facilities may refuse to take part in the study. Following randomization of sampled clinics, we will implement an additional randomization scheme to balance the distribution of the four SP scenarios (MSM only, HIV+ only, MSM and HIV+, and non-MSM HIV- man) and the 8 different SPs across the 20 study clinics. The scheme will also ensure that case scenarios and SP choice will be distributed over the clinic visit duration to balance the potential effects of these design features on our outcome measurement.

Recruitment took place in a staged manner, first at the facility level and then at the provider level. Following sampling and randomization of facilities to the treatment versus control condition (see Section 22.0 for justification of the randomization approach), facility directors of the chosen sites were contacted by [name], a co-investigator on this study and Director of the STD Clinical Quality Control Program at the GDCDC, as well as officials at a subsidiary organization at the Guangzhou City STD Control Center (GZCDC). STD control officials at the GZCDC report to their counterparts at the GDCDC for all matters pertaining to surveillance, disease control, and intervention work. Both [name] and his subordinates at the GZCDC maintain regular contact with administrators

PROTOCOL TITLE: Standardized Patients to Address Intersectional Stigma  
VERSION DATE: 07/23/2019

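### The training-by-script model has no script main effects, so its interaction coefficients measure the care gap inside the trained clinics and not the training's effect on stigma

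*Combined protocol and SAP*

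**What the plan says.** Section 17.3 gives two intention-to-treat regressions for the intervention. The first estimates the overall effect on care quality. It adjusts for the doctor's baseline mean index "as well as a vector of SP and disease script type (varying HIV and MSM status) fixed effects".

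The second serves what the section describes as the real interest: "we are primarily concerned with observing how the training affects the difference in the quality of care received by patients presenting as MSM or HIV-positive". The text says that it follows the earlier regressions, "but interacting the dummy clinic treatment allocation with dummy variables for each SP script type". The printed equation contains:

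- an intercept α₀ and the treatment dummy T (coefficient α₁);
- three products of T with the script dummies V for HIV+/MSM−, HIV−/MSM+ and HIV+/MSM+ (α₁₁, α₁₂, α₁₃);
- the baseline mean (α₂);
- a covariate vector Γ, which "is a vector of SP fixed effects".

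V appears nowhere without T. The section nevertheless says that α₁₁ to α₁₃ "represent the effect of training offer on the *difference* in healthcare quality provided" to the three stigmatised presentations, relative to HIV−/MSM−.

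**The concern.** The stated target is a difference in differences: the script gap in trained clinics minus the script gap in control clinics. A regression can estimate it only if each arm is allowed its own script gap. The printed equation allows a gap in the treated arm alone.

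If that equation is coded as printed, the conclusions go wrong in three ways whenever control clinics treat stigmatised presentations worse:

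- A training with no effect appears to cause stigma.
- A training that abolishes stigma appears to do nothing.
- A training that halves stigma appears harmful.

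The overall coefficient α₁ is distorted as well. The study is a pilot for a later full-scale trial, so a signal with the wrong sign would carry forward.

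**Working it through.** **Cell means of the printed equation.** Hold the baseline mean and SP fixed.

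| Cell | Printed model | With V main effects (δ_k) |
|---|---|---|
| Control, reference script | α₀ | α₀ |
| Control, script k | α₀ | α₀ + δ_k |
| Treated, reference script | α₀ + α₁ | α₀ + α₁ |
| Treated, script k | α₀ + α₁ + α₁k | α₀ + α₁ + δ_k + α₁k |

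In the printed model, α₁k = (treated, script k) − (treated, reference). Control-arm stigma does not enter it. With δ_k added, α₁k = (treated k − treated reference) − (control k − control reference), which is the quantity that the plan describes.

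In the printed model α₁ is the treated reference mean minus the average over all control scripts. With balanced scripts and a gap of −0.5 SD for each stigmatised script, a training with no effect gives α₁ = 0 − (0 − 0.5 − 0.5 − 0.5)/4 = +0.375.

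**Can another term absorb the script effects?**

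- *SP fixed effects.* They could do so only if each SP played a single script. Section 2.1 says "we will randomly vary the HIV infection status and sexual orientation of all of our SPs". Section 5.2 has the script drawn at random for each interaction. Section 12.1 balances the four scripts "and the 8 different SPs across the 20 study clinics". SPs are therefore crossed with scripts.
- *Baseline covariate.* It is a doctor-level average over baseline visits and does not vary with the follow-up script.

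**Simulation inputs.** From Section 17.2: 20 clinics randomised 1:1, 160 visits at 8 per clinic, intra-cluster coefficient 0.07, outcome SD 1. From Section 17.3: OLS with errors clustered by clinic. From Section 12.1: 4 scripts and 8 SPs. Each script was used twice per clinic, and tests were two-sided at 5% against t with 19 df. The documents give no observed stigma gap, so the gaps are assumptions.

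*Control gaps −0.3/−0.3/−0.6 SD, 3,000 runs per scenario. Order: α₁₁/α₁₂/α₁₃.*

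| Training | Truth | Printed model, mean | Printed, rejection | With V, mean | With V, rejection |
|---|---|---|---|---|---|
| No effect | 0/0/0 | −0.30/−0.30/−0.60 | 17%/17%/47% | 0.00/0.00/0.00 | 5–6% |
| Halves gaps | +0.15/+0.15/+0.30 | about −0.15/−0.14/−0.30 | 9%/8%/17% | +0.14/+0.16/+0.30 | 7%/6%/11% |
| Removes gaps | +0.30/+0.30/+0.60 | 0.00/0.00/0.00 | 6–7% | +0.30/+0.31/+0.60 | 10%/10%/25% |

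In all three rows the printed model gives α₁ of about +0.30, against a true value of 0. This agrees with −(0 − 0.3 − 0.3 − 0.6)/4 = +0.30. With V added, α₁ is about 0.

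*Equal gap for every stigmatised script, no training effect, printed model, 1,500 runs per scenario.*

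| Assumed gap | Rejection of the true null, each interaction |
|---|---|
| −0.5 SD | about 35% (α₁k about −0.50, α₁ about +0.37) |
| −0.3 SD | 16–19% |
| −0.18 SD | about 11% |

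**Boundary checks.** With no gap in either arm, the two models agree. Drawing scripts at random, without blocking them within clinics, gives the same results as the no-effect row. If each SP is made to play only one script, the two models coincide, as the algebra predicts.

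**Precision.** There are 160/2/4 = 20 visits per arm and script, with within-clinic variance 1 − 0.07 = 0.93. Ignoring covariates, the standard error of an interaction is √(0.93 × 2/20) = 0.30 in the printed model, which contrasts two cells. It is √(0.93 × 4/20) = 0.43 with V added, which contrasts four. The simulation, with SP and baseline terms, gives about 0.32 and 0.45.

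**The case against.** The strongest reply is that this is a slip of notation. The surrounding prose states the right target, calls the regressions analogous to the earlier ones, and interprets the coefficients correctly. The earlier model does carry script effects, and a competent analyst might restore them without comment. That reading of the intent is plausible. But Γ is a new symbol with its own definition, and no other text puts the script terms back. An analyst who follows the equation gets the wrong quantity. One who adds the terms departs from the written plan. Either way the section contradicts itself and needs correcting.

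Four further points deserve weight:

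- **Priority.** Sections 17.1 and 17.2 call the intervention effect a secondary goal of a pilot. The stigma-quantification model in 17.3 includes the HIV and MSM main effects and is unaffected. Against this, Section 3.1 ties the RCT-phase primary endpoint to the intervention's impact on stigma, and 17.3 names that impact as the goal.
- **Size.** The error scales with a gap that the documents do not report. The only effect sizes in Section 17.2 are 0.17 and 0.18 SD. At −0.18 SD, false rejection is about 11%, well below 35%. The upward bias in α₁ also requires control-arm gaps that are negative on average.
- **Power.** The corrected model is imprecise at 160 visits. Even if training abolishes a 0.5 SD gap, it detects each interaction in only about 19–20% of trials. This is a real limit, but the smaller standard error of the printed model came only from assuming no stigma in control clinics.
- **Participation model.** No interaction equation is printed for the two-stage least squares version, and the earlier two-stage models use the covariate vector that includes script effects. The defect is shown only for the intention-to-treat interaction model.

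**Conclusion.** The concern holds: the model is wrong as written. In the printed equation α₁₁ to α₁₃ estimate the script gap inside the treated arm. They do not estimate the training's effect on that gap, so the equation contradicts the plan's own interpretation. This follows from the algebra for any non-zero control-arm gap, given that SPs are crossed with scripts.

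Only the size rests on assumption. With no training effect, false rejection for each interaction ranges from about 11% at a gap of −0.18 SD to about 35% at −0.5 SD. The estimate is off by the whole control-arm gap in every scenario. The correction is needed before the follow-up data are analysed.

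**What to change.** In Section 17.3, add the three script dummies as main effects to the enacted-stigma equation. Equivalently, define Γ as SP and script-type fixed effects, as X already is in the main intention-to-treat model. α₁₁ to α₁₃ then become the difference in differences that the text describes, and α₁ becomes the training effect for the reference script.

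If the participation version of this model is to be run, print its equation with the same script main effects, so that the point is not left to inference.

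The cost is one line of text and no new data. Each interaction's standard error rises from about 0.32 to about 0.45 SD. The plan should say that these interactions will be imprecise at 160 visits and should be reported mainly as estimates with confidence intervals.
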